8.6.2. Clinical Laboratory Parameters

All clinical laboratory (clinical chemistry, hematology, urinalysis, coagulation, serology, and cytokines) parameters, with changes from baseline, will be listed; any value outside the clinical reference range will be flagged. Separate listings will be provided for any parameter for which there is any individual subject value outside the respective clinical reference range.

Summary tables and boxplots by treatment and timepoint will be provided for clinical chemistry, hematology, serology, urinalysis, coagulation parameters and cytokines, with changes from baseline.

Values recorded as $< x$, $\leq x$, $> x$, or $\geq x$ will be displayed in the listings as recorded. For the derivation of listing flags, calculation of summary statistics, and presentation in the figures, $< x$ and $\leq x$ values will be set to [0/half of x], whereas $> x$ and $\geq x$ values will be set to x.

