3. STUDY ENDPOINTS

3.1. Primary Endpoints

The primary safety endpoints for this study are as follows:

- incidence and severity of adverse events (AEs)
- incidence of laboratory abnormalities, based on hematology, clinical chemistry, and urinalysis test results

- 12-lead electrocardiogram (ECG) parameters
- vital signs measurements
- physical examinations
- anti-CPT31 antibodies, e.g., immunoglobulin (Ig)G, IgM

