8.1.1. Calculation of the Summary Statistics

For continuous data the following rules will be applied:

- Missing values will not be imputed, unless specifically stated otherwise.
- Unrounded data will be used in the calculation of summary statistics.
- If the number of subjects with valid observations (n) < 3 , summary statistics will not be calculated, with the exception of n , minimum, and maximum.
- As Early Termination data is not associated with any scheduled timepoint, it will be excluded from all calculations of summary statistics.

For categorical data the following rules will be applied:

- If the categories of a parameter are ordered (eg, AE severity), all categories between the possible minimum and maximum categories will be included, even if $n = 0$ for a given category. If the categories are not ordered (eg, race), only those categories for which there is at least 1 subject represented will be included.
- Missing values will not be imputed, with the exception of AEs where the 'worst-case' approach will be taken (see [Section 8.6.1](#)), or unless specifically stated otherwise. A 'missing' category will be included for any parameter for which information is missing. This will ensure that the population size totals are consistent across different parameters.

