8.1.3. Repeat and Unscheduled Readings

For vital signs and ECG data only, any predose value recorded in addition to the original value or a postdose value recorded within 15 minutes of the original value will be defined as a repeat value; any postdose value recorded more than 15 minutes after the original value will

be defined as an unscheduled value. For all other data types (eg, laboratory parameters), any value recorded in addition to the original value will be defined as an unscheduled value.

The original value will be replaced by the last associated repeat value in all calculations.

As unscheduled values are not associated with any scheduled timepoint, they will be excluded from all calculations, with the exception of the baseline derivation (see Section 8.1.4).

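### The SAP specifies no count of subjects with a laboratory abnormality, although that incidence is a primary safety endpoint, and its rule on unscheduled values would keep some abnormalities out of such a count

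*SAP*

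**What the plan says.** SAP 3.1 lists among the primary safety endpoints the "incidence of laboratory abnormalities, based on hematology, clinical chemistry, and urinalysis test results"; Protocol 2.2.1 has the same endpoint. Protocol 8.4 adds only that safety data will be listed and described.

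The planned laboratory analysis is in SAP 8.6.2. Values outside the clinical reference range are flagged, and "Separate listings will be provided for any parameter for which there is any individual subject value outside the respective clinical reference range". In addition, "Summary tables and boxplots by treatment and timepoint will be provided for clinical chemistry, hematology, serology, urinalysis, coagulation parameters and cytokines", with changes from baseline. Nothing in that section counts subjects.

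Two general rules bear on any such count. For laboratory data, SAP 8.1.3 says that "any value recorded in addition to the original value will be defined as an unscheduled value", and that "they will be excluded from all calculations, with the exception of the baseline derivation". Under the rules for continuous data, SAP 8.1.1 says: "As Early Termination data is not associated with any scheduled timepoint, it will be excluded from all calculations of summary statistics".

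For results recorded as below a limit x, SAP 8.6.2 says that such "values will be set to [0/half of x" and closes the bracket there. The choice between the two substitutions is still open in a document marked final, and it applies to listing flags, summary statistics and figures.

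**The concern.** An incidence is a number of subjects out of those exposed. By-timepoint summaries and listings do not state it, so the analysis text does not match the endpoint it serves. The rule on unscheduled values would then bias a count made under the SAP's own conventions, because an abnormality seen only on an extra draw would not enter it.

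This matters here because the nonclinical signal was partly sporadic. Protocol 1.4.1 reports one moribund animal with renal tubular degeneration in the 10 mg/kg/day rat group, while 63 of 64 animals at 10 and 20 mg/kg/day tolerated CPT31 well. Protocol 1.4.2 reports renal tubular degeneration with clinical chemistry changes in monkeys. A finding confined to a few subjects is better shown by a subject count than by group averages at each timepoint.

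**Working it through.** The plan gives no sample size or power figure to reproduce. The group arithmetic is consistent: 4 × (6 + 2) = 32, that is 24 on CPT31 and 8 on placebo.

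**1. Endpoint against analysis**
- Adverse events: SAP 8.6.1 counts subjects by treatment, severity and preferred term.
- QTc: SAP 8.6.4 puts each subject's maximum postdose value and maximum increase into categories, using original, repeat and unscheduled values.
- Laboratory abnormalities: SAP 8.6.2 gives by-timepoint summaries, boxplots and listings. Being out of range drives a listing flag but no table.

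The SAP therefore uses subject-level counts for the two neighbouring endpoints and not for this one.

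**2. By-timepoint summaries do not yield the incidence** (assumed values, n = 6)
- Continuous data: one subject at 1.5 × ULN and five at 0.8 × ULN have mean (5 × 0.8 + 1.5)/6 = 5.5/6 = 0.92 × ULN. The mean looks normal while the incidence is 1/6 = 16.7%. A maximum or a boxplot would show the high value.
- Categorical data, such as urinalysis: suppose 1/6 is abnormal at each of two timepoints. If it is the same subject, the incidence is 1/6 (16.7%). If they are two subjects, it is 2/6 (33.3%). The by-timepoint table is identical in both cases.

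**3. Effect of the unscheduled-value rule**
Protocol Appendix 6 schedules postdose laboratory draws on Days 2 to 6 and at Follow-up, 28 to 30 days postdose, so 5 + 1 = 6 draws with none between Day 6 and Follow-up. Protocol 7.3.2 allows extra tests, and Protocol 3.1 allows up to 3 extra visits.
- Abnormal on a scheduled draw, normal on retest: the scheduled value stays in. Extra laboratory values are unscheduled rather than repeats, so they do not replace it. The subject is counted.
- Abnormal only on an extra draw: the value is excluded. The group shows 0/6 where the data hold 1/6, a loss of 16.7 percentage points.

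The documents do not say how often the second case would arise.

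**4. Precision of the missing estimate**
With no affected subjects, the exact two-sided 95% upper limit is 1 − 0.025^(1/n).
- n = 6: 45.9%
- n = 8 (pooled placebo): 36.9%
- n = 24 (all CPT31): 14.2%

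The incidence can be computed at the planned sizes but will be imprecise. The pooled figure spans a 0.24/0.01 = 24-fold dose range, so it does not bound the risk at the top dose.

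**5. The open below-limit rule** (assumed values, n = 6)
- All six values below x: the mean is 0 or 0.5x.
- Three below x and three at 1.5x: (3 × 0 + 3 × 1.5x)/6 = 0.75x, or (3 × 0.5x + 3 × 1.5x)/6 = 1.00x.

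Two programmers could follow the same text and report different results.

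**The case against.** The strongest defence is that most of the signal is already reported. Protocol Appendix 1 treats a clinically significant abnormal laboratory finding as an adverse event, Protocol 7.3.2 has the investigator assess all laboratory data, and SAP 8.6.1 counts the resulting events by subject. SAP 8.1 lists all captured data, so excluded values remain visible and, with 32 subjects, a reader could count cases by hand. This stands, and it limits the point. It does not close it: the adverse event route depends on judgment, and the endpoint is defined on test results and listed separately from adverse events.

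Several stronger readings are tempting but not supported.
- *The endpoint will never be estimated.* SAP section 1 leaves table details to the TFL shells, which were not available. Only the silence of the SAP text can be asserted.
- *The SAP offers only means.* It plans summary tables and boxplots. SAP 8.1.1 also has rules for categorical data, and the minimum and maximum are among its summary statistics.
- *Early-termination samples would certainly be lost.* That exclusion sits under continuous data and does not clearly govern a categorical count. The documents also do not show that retests or termination draws hold the worst values.
- *Dose escalation is exposed.* Protocol 3.6 requires the safety review team to see data from all participants, and Protocol 3.7 sets criteria on numbers of affected subjects. Neither needs this table.
- *The cytokine results show the endpoint failing.* Cytokines are outside this endpoint, and no assay limit or proportion below it is given.

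**Conclusion.** The concern holds in limited form. The SAP text specifies no subject-level incidence for a primary safety endpoint, and 8.1.3 would leave out abnormalities seen only on unscheduled draws. Each subject missed in this way lowers a dose-group incidence by 1/6, or 16.7 percentage points; how many would be missed cannot be known from the documents. The open below-limit rule is a separate, smaller defect.

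This should be fixed, but it does not block the trial. SAP 8.6.6 plans no safety inference, so no alpha or power is affected, and the consequence is confined to what the study report presents. The conclusion assumes that the TFL shells do not already contain such a table. If they do, the SAP still needs to define it and to settle which values count.

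**What to change.** Add to SAP 8.6.2 a table along these lines: *Number and % of subjects with at least one postdose abnormal value, per hematology, chemistry and urinalysis parameter, by treatment. Abnormal means outside the reference range; where a DAIDS v2.1 grade exists for the parameter, also show the worst postdose grade and worsening from baseline. All postdose values are used (scheduled, unscheduled and early termination), as an exception to 8.1.1 and 8.1.3.*

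The reference-range flag already exists in 8.6.2, and the protocol already applies DAIDS v2.1 laboratory grades for eligibility. The condition on grades is needed because the grading table is not in the documents, so it cannot be assumed that every parameter has a grade.

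Replace the bracketed below-limit choice with a single rule before database lock. Either substitution is workable. An all-CPT31 column and a different cytokine summary are optional.

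The cost is SAP wording and one or two extra tables from data already collected. Counts may look slightly higher, because extra draws give more chances to record an abnormal value.

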8.6.3. Vital Signs Parameters

All vital signs parameters, with changes from baseline will be listed; any value outside the clinical reference range will be flagged.

Summary tables and boxplots by treatment and timepoint will be provided for all vital signs parameters, with changes from baseline.

8.6.4. 12-lead Electrocardiogram Parameters

All 12-lead ECG parameters, with changes from baseline, will be listed; any value outside the clinical reference range will be flagged.

Summary tables and boxplots by treatment and timepoint will be provided for all 12-lead ECG parameters, with changes from baseline. An outlier analysis will be performed for QT interval corrected for heart rate using Bazett's formula (QTcB) and QT interval corrected for heart rate using Fridericia's formula (QTcF). The analysis will include all individual original, repeat, and unscheduled postdose values.

The maximum postdose values will be summarized by treatment according to the following categories:

- ≤ 450 ms
- >450 and ≤ 480 ms (all instances flagged in the listing)
- >480 and ≤ 500 ms (all instances flagged in the listing)
- >500 ms (all instances flagged in the listing)

The maximum increases from baseline will be summarized by treatment according to the following categories:

- ≤ 30 ms
- >30 and ≤ 60 ms (all instances flagged in the listing)
- >60 ms (all instances flagged in the listing)

8.6.5. Other Assessments

Medical history will be listed.

All other safety and tolerability assessments not detailed in the above sections will be listed only.

8.6.6. Safety and Tolerability Statistical Methodology

No inferential statistical analyses are planned.

8.7. Immunogenicity Assessments

8.7.1. Immunogenicity Endpoints

The immunogenicity endpoints are anti-CPT31 antibodies, e.g., immunoglobulin (Ig)G, IgM. Immunogenicity samples will be collected on Day 1 predose, Day 2 (24 h), Day 5 (96 h) with an additional immunogenicity sample taken at the Follow-up visit.

8.7.2. Immunogenicity Statistical Methodology

All immunogenicity data will be listed.

The anti-CPT31 antibodies, e.g., immunoglobulin (Ig)G, IgM will be summarized.

Summary tables by treatment and timepoint will be provided for all immunogenicity data.

9. INTERIM ANALYSES

No formal interim statistical analyses are planned for this study.

10. SIGNIFICANT CHANGES FROM THE PROTOCOL-SPECIFIED ANALYSES

There were no significant changes from the protocol-specified analyses.

12. APPENDICES

Appendix 1: Document History

Status, Version	Date of Change	Summary/Reason for Changes
Final, Version 1.0	NA	NA; the first version.

NA = not applicable
